9.1.2 SECONDARY OBJECTIVES

9.1.2.1 SENSITIVITY AND SPECIFICITY IN PREDEFINED SUBGROUPS

| Table 9-3. Projected numbers of clinically significant COPD cases and non-cases we expect by subgroup of interest assuming prevalence of obstructed individuals is between 6-16%. (*Non-Hispanic) This table assumes prevalence of non-clinically significant COPD similar to clinically significant COPD (not included in this table). | | | | | | | | | | |
|--|-------------|-------------|-------------|--------------|--------------|----------------|-------------|-------------|--------------------|---------------------|
| | Total | Men (50%) | Women (50%) | White* (62%) | Black* (15%) | Hispanic (18%) | Rural (46%) | Urban (54%) | Ever-Smokers (40%) | Never-smokers (60%) |
| Projected # confirmed clinically significant COPD by subgroup | 300-800 | 150-400 | 150-400 | 186-496 | 45-120 | 54-144 | 138-368 | 162-432 | 120-320 | 180-480 |
| Projected # confirmed no COPD by subgroup | 3,400-4,400 | 1,700-2,200 | 1,700-2,200 | 2,108-2,728 | 510-660 | 612-792 | 1,564-2,024 | 1,836-2,376 | 1,360-1,760 | 2,040-2,640 |

We will also examine several subgroups of interest that are key to addressing our overall goal of defining the value of CAPTURE across a broad range on individuals. These will include sex, ethnic groups, rural and urban location, and educational level, among individuals with clinically significant COPD, spirometrically defined COPD and individuals with “mild” COPD as defined in this protocol. We have specifically chosen clinical sites with a diverse gender, racial and ethnic mix, and rural and urban mix with the expected prevalence of clinically significant COPD cases and controls by subgroup outlined in Table 9-3, again with corresponding sensitivity and specificity confidence interval widths in Table 9-1. For example, if sensitivity of CAPTURE in Hispanic individuals is 90%, then a sample size of approximately 100 would give a confidence interval of $90\% \pm 5.9\%$. We believe that with an overall sample size of 5,000 recruited patients we will have adequately sized subgroups to assess the operating characteristics of CAPTURE in the subgroups of interest.

9.1.2.2 FURTHER ANALYSIS OF ASSOCIATIONS BETWEEN MEETING COMPOSITE ENDPOINT AND INDIVIDUAL AND PRACTICE LEVEL OUTCOMES

Secondary analyses for evaluating practice behavior are exploratory, and therefore not included in a formal power and sample size analysis. These analyses are described further in Section 9.3.2.

9.2 POPULATIONS FOR ANALYSES

Aim 1

Population used for sensitivity calculations are all enrolled patients with clinically significant COPD as defined by post-bronchodilator $FEV_1/FVC < 0.70$ in addition to either ≥ 1 exacerbation-like event (ECOPD) within the past 12 months or an $FEV_1 < 60\%$ predicted.

Population used for specificity calculations are all enrolled patients with no demonstrable COPD as determined by research spirometry conducted upon study entry, $FEV_1/FVC \geq 0.70$.

Aim 2

Clinician participants: enrolled clinicians are from 2 primary care practices in each of five US PBRN regions that do not engage in Aims 1 or 3 investigation. Eligible clinicians include primary care providers and primary care clinical non-provider support personnel.

Patient participants: enrolled as a sub-sample of Aim 1 participants at baseline. One CAPTURE patient opinion survey is administered at baseline. Aim 2 participants fulfill the inclusion, exclusion and population analysis criteria of aim 1.

Aim 3

Populations used in 2-sample comparisons of outcomes between the two intervention arms will be based on randomization group (intent-to-treat analysis).

For primary analysis of each Aim 3 outcome, the analysis population will consist of all patients with follow-up data for that outcome from both the medical record review and the patient survey administered by the COPD Foundation (section 8.2).

Secondary analyses will be performed using alternative analysis populations, including

1. All patients with outcome data from the medical record review, and
2. All patients selected for follow-up.

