| Endpoints: | 
Aims 1 and 3 Primary Endpoints:
 
Aim 1 –
Sensitivity and specificity of CAPTURE to identify previously undiagnosed patients with clinically significant COPD at baseline.Aim 3 –
Proportion of CAPTURE+ participants who meet at least one of the following within 12 months of study baseline (composite endpoint): 1) referral for or completion of clinical spirometry testing, 2) new diagnosis of COPD, 3) newly prescribed respiratory medication (long acting bronchodilator or anti-inflammatory for respiratory condition), 4) referral to a specialist for respiratory evaluation/treatment, or 5) referral for or completion of pulmonary rehabilitation. 
Aim 2 Primary Endpoints:
 
Primary care clinician recommendations that inform CAPTURE RE-AIM strategies at both provider and clinical support levels of primary care practice.Primary clinician recommendations that inform CAPTURE-associated COPD education models for primary care clinicians.Primary care clinician recommendations that inform CAPTURE-associated COPD clinical quality improvement designs across a variety of primary care practice types. 
Aims 1 and 3 Secondary Endpoints:
 
Aim 1 –
Sensitivity and specificity of CAPTURE to identify previously undiagnosed patients with COPD across sex, ethnic groups, urban vs rural location, and educational level.Positive and negative predictive values (PPV and NPV) in different practice settings.Areas under the receiving operator characteristic curve (AUC) for various cutpoints of CAPTURE and PEF₁ measurements to determine the best cutpoint for COPD+ screen.AUC to identify the combination of patient/site characteristics which best discriminates those with clinically significant COPD.All primary and secondary endpoints as applied to 1) spirometry-defined COPD and 2) mild COPDAim 3 –
Proportion of CAPTURE+ participants who have each of the following occur within 12 months of study baseline (separate endpoints to be evaluated individually): 1-5) each component of the Aim 3 primary endpoint, and 6) recommendation or administration of influenza vaccination. |

| | |
|--------------------------|---|

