9.1.1.1 SENSITIVITY AND SPECIFICITY OF THE CAPTURE TOOL

Primary Hypothesis 1. The CAPTURE tool will exhibit excellent sensitivity and specificity in diagnosing clinically significant COPD as defined by post-bronchodilator FEV₁/FVC < 0.70 in addition to either ≥1 exacerbation-like event (ECOPD) within the past 12 months or an FEV₁ < 60% predicted. Approximately 5000 patients will be enrolled in the study with the expectation that 300-800 of these will have previously undiagnosed clinically significant COPD, identified through research spirometry and documentation of prior respiratory events. Amongst cases, we will calculate the proportion of individuals who are at high risk for clinically significant COPD based on CAPTURE (sensitivity). Similarly, amongst non-cases, we will calculate the proportion of individuals not classified as having clinically significant COPD based on CAPTURE (specificity). Corresponding 95% confidence intervals will be calculated.

Based on our preliminary data drawn from a research setting, we noted 89.7% sensitivity and 93.1% specificity for CAPTURE. Table 9-1 shows the range of sensitivity and specificity 95% confidence interval widths that would result if the true sensitivity or specificity is 85%, 90% or 95% across a range of sample sizes. For instance, if we find 500 individuals with confirmed clinically significant COPD and CAPTURE has 90% sensitivity, then the 95% confidence interval for sensitivity would be 90% ± 2.6%. Similarly, if 4,000 individuals are confirmed to have no evidence of clinically significant COPD and CAPTURE has 90% specificity, then the 95% confidence interval for specificity would be 90% ± 0.9%.

| | | Sensitivity or Specificity | | |
|-------------|--|----------------------------|--------|--------|
| Sample Size | | 85% | 90% | 95% |
| 5000 | | ± 1.0% | ± 0.8% | ± 0.6% |
| 4000 | | ± 1.1% | ± 0.9% | ± 0.7% |
| 1000 | | ± 2.2% | ± 1.9% | ± 1.4% |
| 500 | | ± 3.1% | ± 2.6% | ± 1.9% |
| 250 | | ± 4.4% | ± 3.7% | ± 2.7% |
| 100 | | ± 7.0% | ± 5.9% | ± 4.3% |
| 50 | | ± 9.9% | ± 8.3% | ± 6.0% |

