9.3 STATISTICAL ANALYSES

9.3.1 SENSITIVITY AND SPECIFICITY (AIM 1)

SAS version 9.4 PROC LOGISTIC will be used for computations. Calculations of sensitivity and specificity along with their corresponding 95% confidence intervals assume independent Bernoulli outcomes for each patient. Clinically significant COPD+ and COPD- populations selected for these analyses are described in Section 9.2. CAPTURE+ patients are those with a baseline CAPTURE score ≥ 5 or with a baseline CAPTURE score of 2, 3, or 4 with a low PEF (defined as <350 L/min for males, <250 L/min for females).

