In addition to the primary sensitivity/specificity calculations, sensitivity/specificity and associated 95% confidence intervals will be calculated in predefined subgroups: sex, ethnic subgroups, rural and urban location, and educational status. As part of secondary analyses, receiver operating characteristic (ROC) curve analyses will evaluate different thresholds of the CAPTURE questionnaire score in defining a positive clinically significant + COPD screen, separately and in combination with low PEF characteristics, **and the additional CAPTURE questions**. As part of this exploration, participant and practice level data as well as interactions with the CAPTURE tool results, will be considered as predictors of clinically significant COPD using multivariable logistic regression. Corresponding positive and negative predictive values will be estimated across the range of prevalence percentages seen at the enrolled practices. Model selection in secondary logistic regression analyses will be based on forward selection using maximum likelihood theory, with entry into the model dependent on statistical significance at the 0.05 level. Exploration of this nature has the potential to produce artificially high operating characteristics (area under the curve [AUC], sensitivity and specificity) based on overfitting the data. SAS 9.4 PROC LOGISTIC includes a cross-validation approach to ROC curve analysis [ROCOPTIONS(CROSSVALIDATE)] that we will use when assessing operating characteristics for any new prediction tool that goes beyond the original CAPTURE metric considered in primary analyses. Once a final logistic regression model has been selected, classification thresholds for predicting clinically significant COPD will be described by the investigative team from the cross-validated ROC curve. Calibration plots of observed versus predicted sensitivity, and observed versus predicted specificity, will be conducted across previously specified subgroups of interest (sex, ethnic subgroups, rural and urban location, and educational status).

All of the above analyses will be applied to these additional populations: (1) patients with spirometrically defined COPD and (2) patients with mild COPD.

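### Protocol 9.1.1.1 and 9.2 define the Aim 1 primary specificity differently; under 9.2 it is specificity in patients without COPD, not specificity for clinically significant COPD

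*Protocol*

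**What the plan says.** The Aim 1 primary endpoint (Protocol 1.1) is "Sensitivity and specificity of CAPTURE to identify previously undiagnosed patients with clinically significant COPD at baseline".

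The protocol then gives two specificity populations.

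- Section 9.1.1.1: "amongst non-cases, we will calculate the proportion of individuals not classified as having clinically significant COPD based on CAPTURE (specificity"). Its precision example speaks of 4,000 people without clinically significant COPD.
- Section 9.2: "Population used for specificity calculations are all enrolled patients with no demonstrable COPD as determined by research spirometry conducted upon study entry", with FEV1/FVC of at least 0.70. Sensitivity in 9.2 is taken in patients with clinically significant COPD.

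Section 9.3.1 follows 9.2: "Clinically significant COPD+ and COPD- populations selected for these analyses are described in Section 9.2".

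Table 9-3 has a row for clinically significant COPD and a row for no COPD. Its caption covers the remaining group: "This table assumes prevalence of non-clinically significant COPD similar to clinically significant COPD (not included in this table"). The same caption describes the projection as "assuming prevalence of obstructed individuals is between 6-16" per cent.

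Section 9.3.1 also plans: "All of the above analyses will be applied to these additional populations: (1) patients with spirometrically defined COPD and (2) patients with mild COPD". On predictive values it says only: "Corresponding positive and negative predictive values will be estimated across the range of prevalence percentages seen at the enrolled practices". The SAP (4.1) places Aim 1 outside its scope, so it does not settle which definition applies.

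**The concern.** A patient with post-bronchodilator FEV1/FVC below 0.70, FEV1 at or above 60% predicted and no exacerbation-like event in the past 12 months does not have clinically significant COPD. For that target the patient is a non-case, and a CAPTURE+ result is a false positive. Under 9.2 the patient counts in neither sensitivity nor specificity. Under 9.1.1.1 the patient counts in specificity. Two analysts following the two sections would report different primary numbers under one name.

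This group matters to the purpose of the tool. Protocol 2.1 and 2.2 criticise earlier case finding for picking up mild disease and present CAPTURE as aimed at clinically significant disease. In the development study (Protocol 2.2), 74 of the 161 controls (74 + 87), or 46%, were patients of this kind. Specificity under 9.2 therefore leaves out the non-cases that the tool is most meant to avoid flagging.

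**Working it through.** **The plan's own figures.** Table 9-3 takes the obstructed non-cases to be as numerous as the cases. The no-COPD row is then 5,000 − 2×300 = 4,400 and 5,000 − 2×800 = 3,400, exactly as printed, so 300 to 800 patients are in neither row. All non-cases would number 5,000 − 300 = 4,700 to 5,000 − 800 = 4,200.

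Table 9-1 reproduces with the Wald formula: 1.96×√(0.9×0.1/4,000) = 0.93%, printed as 0.9%. At 90% specificity the half-width is 0.89-1.01% on 4,400-3,400 patients and 0.86-0.91% on 4,700-4,200. Precision is not the issue.

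**Caption.** Cases alone are 300/5,000 = 6% to 800/5,000 = 16%. Cases plus an equal left-out group are 600/5,000 = 12% to 1,600/5,000 = 32% obstructed. The caption's 6-16% therefore fits the cases, not all obstructed patients.

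**Formula for the gap.** Let m be the left-out patients and n0 those with no COPD, with CAPTURE+ rates q and f. Specificity is 1 − f under 9.2 and 1 − (n0·f + m·q)/(n0 + m) among all non-cases. The difference is

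gap = m/(m + n0) × (q − f).

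It is zero if q = f. The documents do not give q, so 20%, 40% and 60% are assumed.

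**Accrual inputs (SAP 13.1).**

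- Practices in Table 6: 15+15+9+6+11+12 = 68. Patients: 663+750+431+280+468+446 = 3,038, or 44.68 per practice.
- Roughly 2 patients per practice have spirometric COPD and about 10 are CAPTURE+.
- n0 = 44.68 − 2 = 42.68. If both obstructed patients are CAPTURE+, f = (10 − 2)/42.68 = 18.7%.
- The split of the 2 obstructed patients is not given. Leaving out 1 or 1.5 of them is assumed.

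| Basis | m | n0 | f | Share left out | Gap in points at q = 20 / 40 / 60% |
|---|---|---|---|---|---|
| Accrual, half of obstructed left out | 1 | 42.68 | 18.7% | 2.3% | 0.0 / 0.5 / 0.9 |
| Accrual, three quarters left out | 1.5 | 42.68 | 18.7% | 3.4% | 0.0 / 0.7 / 1.4 |
| Caption, 6% obstructed, even split | 150 | 4,700 | 18.7% | 3.1% | 0.0 / 0.7 / 1.3 |
| Caption, 16% obstructed, even split | 400 | 4,200 | 18.7% | 8.7% | 0.1 / 1.8 / 3.6 |
| Table 9-3 rows, 12% obstructed | 300 | 4,400 | 6.9% | 6.4% | 0.8 / 2.1 / 3.4 |
| Table 9-3 rows, 32% obstructed | 800 | 3,400 | 6.9% | 19.0% | 2.5 / 6.3 / 10.1 |

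The 6.9% is 1 minus the preliminary 93.1% specificity in 9.1.1.1, used only as an assumption.

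If cases are instead CAPTURE+ at 90% and left-out patients at q, the accrual rows become −0.02 / 0.45 / 0.92 (f = 19.9-20.9%) and −0.06 / 0.65 / 1.35 (f = 20.3-21.7%).

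**Sampling error at f = 18.7%.** With n = 42.68×68 = 2,902, the half-width is 1.96×√(0.187×0.813/2,902) = 1.42 points. At full enrolment, n = 5,000×42.68/44.68 = 4,776 gives 1.11 points. Both assume usable spirometry in everyone, so the real half-widths would be slightly wider.

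**PPV, if it were computed from the 9.2 specificity.** Take one case per practice, 90% sensitivity and p = 1/44.68. Then PPV = 0.9p/(0.9p + f(1 − p)) = 9.90%. On all patients it is 0.9/(0.9 + 8 + q) = 9.89 / 9.68 / 9.47% at q = 20 / 40 / 60%.

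**The case against.** The strongest reply is that little is lost. Section 9.1.1.1 already names the all-non-case measure. Section 9.2 and the Table 9-3 caption are open about the restriction. Sensitivity for mild COPD is a planned endpoint with a confidence interval, and it is the CAPTURE+ rate in nearly all left-out patients. The mild-COPD definition requires no prior history of exacerbation rather than none in 12 months, and the spirometric-COPD analysis covers that remainder. On accrual figures the gap is about the size of sampling error. Nothing says that PPV and NPV will use the 9.2 restriction.

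Most of this stands, and it limits the size of the point. It does not remove it. Section 9.3.1 sends the analyst to 9.2, so the 9.1.1.1 definition would not be the one applied. In the mild-COPD and spirometric-COPD analyses the target changes, so a CAPTURE+ result in a left-out patient becomes a true positive. The all-non-case specificity could be pieced together from those outputs, but no section plans to report it next to the primary figure.

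A reader might infer from the last table row that specificity will be overstated by about 10 points. The documents do not support that. It needs 32% obstructed, against 2/44.68 = 4.5% at accrual. It also needs f = 6.9%, which does not fit accrual: 0.069×42.68 = 2.9, plus at most 2 obstructed, gives 4.9 CAPTURE+ per practice rather than 10. It would be equally wrong to infer that the left-out patients are never analysed.

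**Conclusion.** The inconsistency is real and concerns a primary endpoint. If 9.2 is followed, the figure reported is specificity in patients without COPD.

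The likely effect is small: about 0 to 1.4 points on accrual figures, against a half-width of 1.4 points at accrual size and 1.1 at full enrolment. Only the most extreme accrual scenario exceeds the latter. The gap is a difference in what is estimated, so a larger sample would not remove it.

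The size rests on an assumed q, an assumed split of the obstructed patients, and two rounded per-practice figures from a power memo. It would be larger only if obstruction were as common as Table 9-3 projects.

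The likely direction is a more favourable specificity, but this is not established. It rests on one sentence in Protocol 2.2, which says that performance was better against controls without COPD. That sentence follows the account of the five-item questionnaire, in a case-control sample, before PEF is added.

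**What to change.** 1. Reconcile 9.1.1.1 with 9.2 so that one primary specificity population is stated.
2. Baseline data already exist: SAP 9.5 reports that by 21 March 2023 follow-up was complete at sites holding about 84% of followed patients, before protocol version 8.0 of 17 July 2023. Keep the 9.2 figure, therefore, and label it *specificity in patients without COPD*.
3. Beside it report, with a 95% CI, the specificity in all patients with adequate spirometry who do not meet the clinically significant COPD definition.
4. State that PPV and NPV for clinically significant COPD use that all-non-case population.
5. Correct the Table 9-3 caption: its rows imply 12-32% obstructed, not 6-16%.

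If the all-non-case figure is made primary instead, disclose that the change was made after data collection.

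The cost is a few sentences, one extra row, no new data, and a reported specificity that may be slightly lower. Labelling the 9.2 figure and adding the row changes no primary analysis.

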9.3 STATISTICAL ANALYSES

9.3.1 SENSITIVITY AND SPECIFICITY (AIM 1)

SAS version 9.4 PROC LOGISTIC will be used for computations. Calculations of sensitivity and specificity along with their corresponding 95% confidence intervals assume independent Bernoulli outcomes for each patient. Clinically significant COPD+ and COPD- populations selected for these analyses are described in Section 9.2. CAPTURE+ patients are those with a baseline CAPTURE score ≥ 5 or with a baseline CAPTURE score of 2, 3, or 4 with a low PEF (defined as <350 L/min for males, <250 L/min for females).

In addition to the primary sensitivity/specificity calculations, sensitivity/specificity and associated 95% confidence intervals will be calculated in predefined subgroups: sex, ethnic subgroups, rural and urban location, and educational status. As part of secondary analyses, receiver operating characteristic (ROC) curve analyses will evaluate different thresholds of the CAPTURE questionnaire score in defining a positive clinically significant + COPD screen, separately and in combination with low PEF characteristics, **and the additional CAPTURE questions**. As part of this exploration, participant and practice level data as well as interactions with the CAPTURE tool results, will be considered as predictors of clinically significant COPD using multivariable logistic regression. Corresponding positive and negative predictive values will be estimated across the range of prevalence percentages seen at the enrolled practices. Model selection in secondary logistic regression analyses will be based on forward selection using maximum likelihood theory, with entry into the model dependent on statistical significance at the 0.05 level. Exploration of this nature has the potential to produce artificially high operating characteristics (area under the curve [AUC], sensitivity and specificity) based on overfitting the data. SAS 9.4 PROC LOGISTIC includes a cross-validation approach to ROC curve analysis [ROCOPTIONS(CROSSVALIDATE)] that we will use when assessing operating characteristics for any new prediction tool that goes beyond the original CAPTURE metric considered in primary analyses. Once a final logistic regression model has been selected, classification thresholds for predicting clinically significant COPD will be described by the investigative team from the cross-validated ROC curve. Calibration plots of observed versus predicted sensitivity, and observed versus predicted specificity, will be conducted across previously specified subgroups of interest (sex, ethnic subgroups, rural and urban location, and educational status).

All of the above analyses will be applied to these additional populations: (1) patients with spirometrically defined COPD and (2) patients with mild COPD.

